### **6.3 Multicenter Analysis**

Approximately 50 centers are planned in this study; whenever possible, approximately 16 subjects will be enrolled per center. In the event a center has a low (< 16) number of subjects enrolled or no subject that meets either of the IGA co-primary endpoints, pooling of centers may be performed based on geographical center location until the pooled center has at least 16 subjects and at least one subject with an IGA of clear or almost clear and at least one subject with a 2 point reduction in IGA.

Centers that do not meet above criteria will be pooled according to the following priorities:

1. Within a state/territory/country;
2. Across states/territory/country.

The exact pools will be determined prior to unblinding according to the above methodology.

Descriptive summary statistics will be generated including center and pooled-center (when appropriate) by co-primary and secondary efficacy endpoints.

### **6.4 Unscheduled Data**

Unscheduled data will not be used in the analyses, but will be presented in the listings.

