7.3.2 Study Procedures by Visit

Visits following the Baseline Visit are to occur at the end of Weeks 1, 3, 6, 9, and 12 (Final Treatment Visit) and a follow up visit at Week 16. However, all interim study visits and the follow up Week 16 study visit may be conducted (on an individual subject basis) up to 3 days before or after the regularly scheduled study visit. An unscheduled visit may occur in the event that the investigator determines that the subject should be seen for safety or any other reasons.

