7.5.3 Clinical Laboratory Testing

Blood samples (approximately 11 mL) will be collected at Screening and the Week 12 Visit (Early Termination, or Final Visit), for hematology and chemistry laboratory analysis (total expected volume of approximately 22 ml). A central laboratory will perform the sample analysis for all study sites. Instructions for sample collection, preparation, labeling, and shipping will be provided by the laboratory.

All laboratory values that are considered clinically significant will be reported as an adverse event and followed as such. The laboratory tests will include the following parameters:

- Hematology: Complete blood count (CBC), including hemoglobin, hematocrit, red blood cell (RBC), white blood cell (WBC), count with differential, and platelet count.
- Blood Chemistry/Lipids: sodium, potassium chloride, bicarbonate or carbon dioxide, glucose, blood urea nitrogen (BUN), creatinine, calcium, uric acid, total bilirubin, total protein, albumin, aspartate aminotransferase (AST), alanine aminotransferase (ALT), alkaline phosphatase, gamma glutamyl transferase (GGT), total cholesterol, high-density lipoproteins (HDL), low-density lipoproteins (LDL), triglycerides, and lactic dehydrogenase (LDH).

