#### **5.4.4 Safety Analysis**

Adverse events will be categorized by system organ class and Preferred Term from the current version of MedDRA. Treatment-emergent adverse events will be summarized overall and by seriousness, by severity, and by relationship to treatment using frequencies and percentages. Adverse events will be considered treatment-emergent if the onset date is on or after the first dose of study medication.

Changes from baseline in vital signs and laboratory parameters, and shifts from baseline laboratory parameters will be summarized by treatment.

Safety summaries will be presented for the double-blind study period. Additional summaries will be presented for the 4 week follow-up study period, based on the treatment received during the double-blind study period.

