#### **6.1 Baseline and Follow-Up Visits**

Visits and timepoints (Baseline; Interim visits [Weeks 1, 3, 6, 9], final double-blind visit [Week 12], and Follow-up visit: [Week 16]) for all analyses will be as record on the eCRFs, except as noted below. Baseline will be the later of the non-missing values from the Screening and Baseline/Day 1 visits scheduled to occur prior to receiving study medication. Unscheduled visits will not be used in for any analyses but will be included on data listings.

If a subject does not complete the study, the final double-blind visit (Week 12) will be reassigned to a scheduled visit based on the relative day ranges in the following table. If a result already exists for the calculated visit or the calculated visit was not a scheduled visit, the next scheduled visit will be assigned.

Study Day Range	Calculated Visit
$2 \leq \text{Study Day} \leq 15$	Week 1
$16 \leq \text{Study Day} \leq 32$	Week 3
$33 \leq \text{Study Day} \leq 53$	Week 6
$54 \leq \text{Study Day} \leq 74$	Week 9
$\text{Study Day} \geq 75$	Week 12

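### The SAP bars unscheduled data from all analyses with no safety exception, so off-schedule laboratory results appear only in listings and are absent from the shift and change summaries

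*SAP*

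**What the plan says.** The exclusion appears twice in the SAP's data handling conventions. Section 6.4 reads "Unscheduled data will not be used in the analyses, but will be presented in the listings". Section 6.1 is worded more broadly: "Unscheduled visits will not be used in for any analyses but will be included on data listings". Section 6.0 introduces these as the conventions for carrying out the statistical analyses, without separating efficacy from safety.

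The safety output they act on is described in SAP 5.4.4: "Changes from baseline in vital signs and laboratory parameters, and shifts from baseline laboratory parameters will be summarized by treatment". No table of worst or any-time post-baseline values is planned.

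Protocol 7.3.2 explains why off-schedule data can exist: "An unscheduled visit may occur in the event that the investigator determines that the subject should be seen for safety or any other reasons". Protocol 7.5.3 fixes the laboratory schedule: samples "will be collected at Screening and the Week 12 Visit", with the early-termination visit counting as the latter. The same section provides another route into the tables: "All laboratory values that are considered clinically significant will be reported as an adverse event and followed as such".

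**The concern.** Safety is the first reason the protocol gives for an unscheduled visit, and laboratory tests are otherwise sparse. If a sample is drawn at such a visit, it may be the only on-treatment value that shows a transient abnormality. Under SAP 6.1 and 6.4 that value cannot enter the shift or change tables. If the Week 12 sample is normal, the subject is tabulated as having had no shift.

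At stake is the completeness of the one laboratory comparison between arms that does not depend on an investigator classifying a value as clinically significant. Listings keep the data but do not compare the arms.

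**Working it through.** The documents state no figure on this point, so the check sets the rules beside the schedule and traces where a result can go.

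**Step 1: scope of the rule.** SAP 6.1 refers to any analyses and SAP 6.4 to the analyses. Neither is limited to efficacy or to by-visit tables. Protocol 7.7.12 plans laboratory and vital-sign summaries without excluding unscheduled values, and SAP 7.0 does not list the exclusion among its changes from the protocol.

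**Step 2: scheduled assessments** (Protocol 7.3.1, 7.5.2, 7.5.3).

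| Visit | Haematology and chemistry | Vital signs |
|---|---|---|
| Screening | yes | yes |
| Baseline/Day 1 | no | no |
| Weeks 1, 3, 9 | no | no |
| Week 6 | no | yes |
| Week 12 or early termination | yes | yes |
| Week 16 | no | yes |

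Laboratory tests have 2 scheduled time points, so 2 − 1 = 1 after baseline. Vital signs have 4, so 4 − 1 = 3 after baseline. The argument therefore bears on laboratory tests much more than on vital signs.

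**Step 3: early termination.** Protocol 7.2.3 has subjects who stop during the double-blind period undergo the Week 12 procedures, which include blood samples. SAP 6.1 reassigns that visit by study day, and moves it to the next scheduled visit where the calculated one was not scheduled. No laboratory test is scheduled at Weeks 1, 3, 6 or 9, so on a natural reading the early-termination result is carried to Week 12 and is tabulated. It is not lost as unscheduled data.

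**Step 4: where an abnormality found at an unscheduled visit can go.**

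- Judged clinically significant: it is reported as an adverse event (Protocol 7.5.3). SAP 5.4.4 defines treatment-emergent events by onset date, so it is tabulated.
- Still present at the Week 12 or early-termination sample: that scheduled value enters the shift table.
- Neither: the result appears in a listing only.

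Only the third path is a gap.

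**Step 5: does any other planned table close it?** No. SAP 5.4.4 has no worst-value table. SAP 5.4.5 and Protocol 7.7.13 promise a laboratory summary for the follow-up period, but no laboratory sample is scheduled at Week 16. A follow-up result would normally be unscheduled and so barred by 6.4, which leaves that summary without scheduled follow-up data.

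**Step 6: size.** Neither document schedules haematology or chemistry at an unscheduled visit. The only test named for one is a urine pregnancy test (Protocol 7.5.5). The number of results on the third path cannot be derived from the documents and may be small.

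**The case against.** The strongest reply is that little is lost. Clinically significant values reach the adverse event tables, persisting abnormalities reach the shift table, early-termination samples are tabulated, and everything else is listed. Scheduled-visit tables also keep the number of assessments comparable between arms, which a worst-value table does not. The rule applies equally to both arms of a double-blind trial, and no between-arm bias has been shown. Safety output is descriptive, and SAP 5.4.2 treats the analyses as exploratory after enrolment stopped. Since an unscheduled visit itself depends on the investigator, a worst-value table is not free of judgement either.

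Most of this stands, and it makes the point minor. It does not remove it. Whether to see a subject and whether to call a value clinically significant are separate decisions, and the documents give no criteria for the second. A worst-value table would show results that were obtained but not so classified. The exploratory status does not make an incomplete laboratory summary more informative.

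Two stronger readings are tempting. A reader might infer that safety data from unscheduled visits drop out altogether, adverse events included. The onset-date rule in SAP 5.4.4 points the other way, although the wording of 6.4 is loose enough to need clarifying. A reader might also infer that most transient abnormalities are lost through this rule. If onset is taken as uniform over the 84 treatment days, an abnormality assumed to last 7, 14 or 28 days is present at Week 12 with probability 7/84 = 8%, 14/84 = 17% or 28/84 = 33%. Those figures rest on assumed durations and describe the sparse sampling schedule, not SAP 6.1 or 6.4. An abnormality that prompts no visit yields no sample, and changing the SAP would not recover it.

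**Conclusion.** The point holds in a limited form and is minor. As written, SAP 6.1 and 6.4 keep any laboratory result from an unscheduled visit out of the shift and change summaries, and no other planned laboratory table brings it back. The abnormalities that go untabulated are those not judged clinically significant and resolved by the Week 12 or early-termination sample. The documents do not allow a count.

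This rests on two readings: that early-termination laboratory results are carried to Week 12 under SAP 6.1, and that adverse events are included by onset date regardless of visit. If either were not intended, the gap would be wider, which is a further reason to state both explicitly.

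**What to change.** - Reword SAP 6.1 and 6.4 so that the exclusion covers efficacy analyses and by-visit summaries only.
- In SAP 5.4.4, add a laboratory shift table from baseline to the worst post-baseline value, including unscheduled results. Keep the by-visit tables on scheduled visits. A matching vital-sign table is optional, since those are already scheduled at Weeks 6, 12 and 16.
- Footnote the new table: subjects with more assessments have more chances of an abnormal value.
- State that adverse events are included by onset date, whichever visit recorded them.
- Reconcile the follow-up laboratory summary in SAP 5.4.5 and Protocol 7.7.13 with the schedule, which has no Week 16 laboratory sample.

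The cost is SAP wording and minor programming on data already due to be listed. The drawback is the unequal number of assessments per subject, which the footnote discloses but does not remove.

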## **7.0 Changes from Protocol**

The following changes were made to the analyses planned in the protocol. These changes were due to the discontinuation of enrollment following the interim analysis and subsequent decision to consider all analyses as exploratory in nature.

- The PP population was removed.
- Multiplicity adjustments were removed.
